## 6.2.3 Bioelectric Impedance

Single frequency bioelectric impedance (BIA) assessments should be performed at baseline and at months F4, and F12 visits. BIA is not required on randomization. All measurements should be conducted in the recumbent position, and should be performed immediately prior to a mid-week HD treatment (i.e., Wednesday or Thursday) and after at least two consecutive dialysis treatments for patients in the nocturnal arm of the study. BIA is not required for patients with bilateral amputations or who have metallic implants such as a pacemaker.

### 6.2.4 Medications

All medications will be recorded using the WHO DRUG system at baseline and at months 4, 8 and 12. Dose levels and frequency of use will be recorded for EPO and phosphate binders at these same time points. For other medications the name of the medication (but not dose or frequency) will be recorded.

# Table 9. Nocturnal Trial - Summary of Data Collection Schedule

A. Health-related Quality of Life/Physical Function, Depression, Cognitive Function, and Treatment Burden Measures\*

Measurement	Central Telephone Interview	Baseline	1 mo	2 mo	3 mo	4 mo	5 mo	6 mo	7 mo	8 mo	9 mo	10 mo	11 mo	12 mo
SF-36 Survey, v2	Yes	~				~								~
Health Utilities Index –3	Yes	✓				~								~
Feeling Thermometer	No	~				~								~
MOS Sleep Scale	Yes	~				~								~
Beck Depression Inventory, v1	Yes	~				~								~
Trailmaking Test B	No	~				~								~
Modified Mini-Mental Status	No	~				~								~
Physical Function	No	~				~								~

\*All physical and cognitive testing should be done pre-dialysis, mid-week within 2 weeks of scheduled time.

Measurement	Blinded Reading	Baseline	1 mo	2 mo	3 mo	4 mo	5 mo	6 mo	7 mo	8 mo	9 mo	10 mo	11 mo	12 mo
Cardiovascular and blood pressure														
Cardiac cine-MRI	Yes	✓												~
Predialysis and postdialysis systolic and diastolic blood pressures*	No	√	✓	✓	~	✓	✓	✓	✓	✓	✓	✓	✓	~
Predialysis and postdialysis weight*	No	$\checkmark$	$\checkmark$	✓	~	✓	✓	✓	$\checkmark$	✓	$\checkmark$	✓	✓	~
Interdialytic hypotensive episodes*	No	✓	√	√	~	√	√	√	√	~	√	√	√	~
Home blood pressure monitoring	No	✓				√								~
Nutrition														
Protein catabolic rate	Yes	✓	$\checkmark$	✓	✓	~	$\checkmark$	~	$\checkmark$	✓	$\checkmark$	~	~	~
Bioimpedance	No	$\checkmark$				$\checkmark$								~

## B. Cardiovascular, Blood Pressure, and Nutritional/Inflammatory Measures (for labs and medications, see Part C below)

\*These measures taken at each kinetic modeling session. Additional measurements from dialysis sessions over the prior 1-week interval also recorded once during baseline, and monthly during follow-up.

## C. Laboratory Measurements and Medications

Measurement	Baseline	1 mo	2 mo	3 mo	4 mo	5 mo	6 mo	7 mo	8 mo	9 mo	10 mo	11 mo	12 mo
Predialysis serum albumin	~	~	~	~	~	~	~	~	~	~	~	~	~
Pre and post-dialysis serum phosphate, creatinine, urea	~~	~	~	~	~	~	~	~	~	~	~	~	~
Interdialytic urine for urea, creatinine, phosphate	~				~								~
Pre-dialysis hemoglobin, calcium, bicarbonate, sodium, and potassium	~	~	~	~	~	~	✓	~	~	✓	~	✓	~
Pre-dialysis transferrin and ferritin 	~		✓			~			✓			✓	
Pre-dialysis parathyroid hormone 	~		✓			~			~			✓	
Intravenous iron (cumulative monthly dose)	~	✓	~	~	~	✓	✓	~	~	✓	~	~	✓
Erythropoietin/Darbopoetin (route, frequency,	~				~				~				~
IV vitamin D metabolites (frequency, weekly dose)	~				~				✓				✓
Phosphorus binders (daily dose)	~				~				~				~
All other medications (including	~				~				✓				~
Serum/plasma samples for biorepository	~				$\checkmark$								$\checkmark$

These local labs to be entered into database at least once every 3 months (center may optionally enter these labs at additional time points)

#### D. Mineral Metabolism and Anemia Measures – see Labs and Medications Table 11C

E. Events (hospitalizations, access complications, survival, discontinuation of the intervention) will be collected throughout follow-up

				•	-								
Measurement	Baseline	1 mo	2 mo	3 mo	4 mo	5 mo	6 mo	7 mo	8 mo	9 mo	10 mo	11 mo	12 mo
Adherence to Therapy													
Number of missed sessions (over 1 month)	~	~	~	~	~	~	~	~	~	~	~	~	~
Number of shortened treatments (over last week)	~				~				~				~
Burden of Treatment													
Minutes to recovery question	~				~								~
Modality preference question	~				~								~
Characterizing the Non-dialytic as	pects of th	ne In	terve	ntior	1								

# F. Treatment Burden, and Characterizing the Non-dialytic Aspects of the Intervention

Patient interviews/questionnaires	~				✓								✓	
-----------------------------------	---	--	--	--	---	--	--	--	--	--	--	--	---	--

# 6.2.5 Local Laboratory Measurements from Kinetic Modeling Sessions

Blood will be drawn pre- and post-dialysis at each kinetic modeling session. Samples will be refrigerated and then shipped to the local laboratory associated with the dialysis unit. See Section 6.1 and Table 11 B for frequency with which various labs will be drawn. In addition, at baseline, and at the F4 and F12 visits, the patient's urine will be collected for the period in between HD sessions along with the time of collection for assessment of urea, creatinine, and phosphate excretion rates.

It is recommended that serum albumin will be measured using the bromcresol green assay, as this is the most widely used measure of albumin in the US. Laboratory parameters which are not obtained as part of the dialysis units usual patient care will be specifically ordered, and costs will be paid by the Study.

It is anticipated that most patients will have all labs in baseline and follow-up drawn at the home training unit where the clinical center is located. However, if it is anticipated that a patient will have baseline and/or follow-up labs drawn at a site other than the home training unit (for example, due to travel considerations), then those patient's labs instead will be sent to the central laboratory for analysis.

## 6.2.6 Questionnaires

The SF-36, Beck Depression Inventory, sleep scale, and other quality of life questionnaires will be administered centrally by trained telephone interviewers blinded to treatment allocation. Patients will be contacted in their homes at baseline and at months 4 and 12. Questionnaires that cannot be administered by telephone due to the need for visual cues (i.e., Feeling Thermometer, Trails B, Modified Mini-Mental Status, burden of treatment) will be administered by the local study coordinator.

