Since the intervention, by necessity, is unblinded, significant efforts will be made to reduce bias. These include: standardization of interventions, blinding interviewers, blinding the assessment of subjective outcomes, in addition to collecting objective outcomes. Patients will be treated and followed for 12 months. Two co-primary outcomes are designated: 1) a composite of mortality with the change over 12 months in the SF-36 RAND physical health composite, and 2) the change over 12 months in left ventricular mass. In addition, first priority secondary outcomes have been designated for seven outcome domains: 1) cardiovascular structure and function (change in LV mass), 2) physical function (change in the PHC), 3) depression/burden of illness (change in Beck Depression Inventory), 4) nutrition (change in serum albumin), 5) cognitive function (change in the Trailmaking Test B), 6) mineral metabolism (change in average predialysis serum phosphorus), and 7) clinical events (rate of non-access hospitalization or death). Hypertension and anemia are also main outcome domains, but without designation of single first priority outcomes. The cost-effectiveness of the two interventions will also be compared.

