## 3.3 Methods to Protect Against Bias

Guidelines for dialytic and non-dialytic co-interventions have been stipulated (see Section 3.4) to reduce the risk that health care team enthusiasm for the novel therapy of nocturnal hemodialysis may lead to differences in care between the treatment groups. To reduce the risk that study personnel may influence patient responses to questionnaires, the HRQL, depression, and utility questionnaires will be administered centrally over the telephone by trained interviewers who are blinded to the patient's treatment assignment. Secondary outcomes that require in-person interviewer survey assessment will be administered by a study coordinator using standard scripts.

Patients on nocturnal home hemodialysis may perceive improvements in their HRQL which have more to do with the novelty of the therapy than to its true benefits ('honeymoon effects'). For this reason, the HRQL outcomes will be assessed at months 4 and 12. HRQL benefits due solely to the novelty of nocturnal hemodialysis would not be expected to persist over one year.

Due to increased opportunity for ultrafiltration, patients on nocturnal hemodialysis may have lower extracellular volume (ECV) than patients receiving HD three times per week. As a result, increases in blood concentrations of albumin, hemoglobin and biochemical parameters may be the result of normalization of ECV rather than true changes in these parameters. To limit volume-related confounding, left-ventricular mass will be assessed by MRI as this method is less subject to volume effects than is echocardiography.

Kt/V calculations may be affected by temporal proximity and amount of protein ingested before dialysis. To account for the possibility of this factor, the study will collect limited information about meal habits before and during dialysis.

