## 5.1.5.7 Treatment Burden and Experience with Nocturnal Hemodialysis

The primary assessment of treatment burden will be based on the question: "How long does it take you to recover from a dialysis session in minutes?" This question was asked as part of a "Dialysis Symptom and Fatigue" questionnaire given to patients participating in the London Daily/Nocturnal HD Study [Heidenheim, 2003]. The other components of the "Dialysis Symptom and Fatigue" questionnaire had previously been validated [Lindsay, 1994] and were part of a battery of established QOL tools used in the London Study. The investigators of the London Daily/Nocturnal HD Study have reported that this question was successfully answered on 313 of 314 occasions. This single question instrument was positively correlated with subscales evaluating fatigue, disease stress, and psychosocial stress, and was negative correlated with the SF-36 physical and mental component summary scores. The instrument also had a high test-retest correlation of r = +0.86 over a 3-month time interval. The London Daily/Nocturnal HD Study indicated large reductions in recovery time were observed on both the daily and nocturnal dialysis therapies after patients switched to these therapies from conventional 3 times per week dialysis. This question will be asked at baseline, months 4 and 12.

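### The minutes-to-recovery question goes to the local coordinator on a visual-cue ground that does not fit it, so a self-reported burden item loses the trial's blinded interview

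*Protocol*

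**What the plan says.** Protocol section 6.2.6 divides the questionnaires into two groups. The SF-36, the Beck Depression Inventory, the sleep scale and other quality-of-life instruments are given centrally by telephone interviewers blinded to allocation, at baseline and months 4 and 12. The second group is described as "Questionnaires that cannot be administered by telephone due to the need for visual cues". It ends with the burden items: "Feeling Thermometer, Trails B, Modified Mini-Mental Status, burden of treatment) will be administered by the local study coordinator".

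Section 5.1.5.7 defines the burden measure. It begins "The primary assessment of treatment burden will be based on the question", and the question is "How long does it take you to recover from a dialysis session in minutes". It is to be asked at baseline and months 4 and 12. Table 9 lists "Minutes to recovery question" in its burden-of-treatment block, beside a question on modality preference.

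Two other sections set the standard for subjective outcomes. Section 2.2 counts among the measures against bias in this open trial "blinding interviewers, blinding the assessment of subjective outcomes". Section 3.3 explains why questionnaires are given centrally: "To reduce the risk that study personnel may influence patient responses to questionnaires". It leaves to the coordinator those secondary outcomes that need an in-person interviewer, and these follow standard scripts.

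**The concern.** The reason given for in-person administration does not describe the question. A single question with a numeric answer can be asked by telephone as readily as an SF-36 item. Sending it to the coordinator takes an entirely self-reported outcome out of the blinded interview, and the protocol offers no other ground for doing so.

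What is at stake is interviewer influence on the main measure of treatment burden. The safety objective in section 2.1 gives patient burden particular emphasis, so the item has some weight. Patients cannot be blinded in this trial. Who asks the question is therefore one of the few sources of bias in this measure that the design can control.

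**Working it through.** No arithmetic is needed to establish the point, and the plan states no figure to reproduce. The check is a comparison of sections.

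1. **Does the section 6.2.6 label cover this question?** Yes. Table 9 places minutes to recovery under burden of treatment, the term used in section 6.2.6. Table 8 also lists it under treatment burden.

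2. **Does the visual-cue reason fit?** It fits other members of the list. The Feeling Thermometer is a visual analog scale (section 5.1.5.2.3), and Trails B is a timed line-drawing task (section 5.1.3.2). For minutes to recovery, section 5.1.5.7 describes a single-question instrument and mentions no card, scale or picture. The reason does not fit.

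3. **Does another stated rule send it to the coordinator?** Section 2.7 gives the coordinator measures that need visual and motor assessment. Section 3.3 gives the coordinator outcomes that require in-person assessment. Nothing in section 5.1.5.7 puts the question in either class.

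4. **Does the coordinator know the arm?** The protocol does not say so outright, but it is a fair inference. Under section 2.9 the investigator or the coordinator runs the randomization program, the assignment appears on screen, and it is emailed to the center. Baseline studies are completed before randomization, so the exposure concerns the month-4 and month-12 answers.

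5. **Is a blinded alternative already running?** Yes. The time points coincide:

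| | Baseline | Month 4 | Month 12 | Asked by |
|---|---|---|---|---|
| Central interview (6.2.6) | yes | yes | yes | blinded telephone interviewer |
| Minutes to recovery (5.1.5.7, Table 9) | yes | yes | yes | local coordinator |

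These are the same time points, not the same visits: the interviewer contacts the patient at home.

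6. **Where does the outcome rank?** It is not one of the two co-primary composites (section 9.3) or a main secondary outcome (section 9.4, Table 7). Table 8 puts it in a separate block, outside the nine outcome domains.

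**The case against.** Four arguments stand on the other side.

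- **Low rank.** The word primary in section 5.1.5.7 applies only within treatment burden. Section 9.4 treats even non-main outcomes inside the domains as exploratory. Other burden signals are also collected: modality change, missed treatments and shortened treatments. This stands, and it limits the importance of the point.
- **Existing safeguard.** Section 3.3 requires standard scripts for in-person items. A script constrains one fixed question with a numeric answer fairly well. This stands in part: a script fixes the wording, but the person asking still knows the arm. The protocol did not rely on scripts alone for the quality-of-life, depression and utility questionnaires.
- **Patients know their treatment whoever asks.** This is true, so a blinded interviewer would remove interviewer influence but not patient reporting bias. The same holds for the SF-36, which the protocol nevertheless gives to blinded interviewers.
- **Risk to a co-primary component.** An answer or a stray remark at month 4 could reveal the arm to someone who later conducts the month-12 SF-36, which feeds the physical health composite. The protocol does not say that different interviewers make the two calls. The risk is real but small: the question would come last, the calls are 12 − 4 = 8 months apart, and the same call already includes a sleep scale. The protocol does not give this as its reason for in-person administration.

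A reader might go further and infer that the false-positive rate for this item is materially inflated. With an assumed 36 patients per arm (80% of 45) and no true effect, the noncentrality is d × √(36/2), where d is the shift in SD units in one arm. Shifts of 0.2, 0.3 and 0.4 SD give 0.85, 1.27 and 1.70. On 70 degrees of freedom, a two-sided 5% test then rejects with probability 13%, 24% and 39%. These figures are purely illustrative. The documents give no interviewer effect, the calculation attributes the whole shift to the coordinator, and the outcome carries no confirmatory alpha. They do not measure a defect in this trial.

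**Conclusion.** The point holds as a limited design flaw. The reason in section 6.2.6 does not apply to the minutes-to-recovery question as section 5.1.5.7 defines it. A self-reported outcome therefore loses blinded interviewing that sections 2.2 and 3.3 adopt and that the trial already provides at the same time points.

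Its size cannot be stated from the documents. It affects one lower-tier outcome, is partly mitigated by scripts, and leaves the co-primary and main secondary conclusions untouched. A reader might take the word primary to mean that a headline result is exposed, but sections 9.3 and 9.4 rule that out.

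The conclusion rests on two assumptions: that the coordinator knows the assignment, inferred from section 2.9, and that the question uses no visual aid beyond what section 5.1.5.7 describes.

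**What to change.** Remove the minutes-to-recovery question from the coordinator list in section 6.2.6. Ask it as the last item of the blinded central telephone interview at baseline, month 4 and month 12, after the SF-36, Health Utilities Index, Beck Depression Inventory and sleep scale. Include baseline so that change from baseline is not mixed with a change of mode. State the mode in section 5.1.5.7 and in Table 9. Leave the modality-preference question with the coordinator, because it could reveal the arm.

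To protect the month-12 SF-36, have a different central interviewer make that call where possible, or do not show the interviewer the earlier answers.

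The cost is one extra question in an existing call, some attention to interviewer assignment, and the small residual risk of unblinding. If the investigators judge that risk too high, the least they should do is replace the visual-cue reason with the real one and acknowledge that this item is not collected by a blinded interviewer.

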# 6.2.7 Objective Tests of Physical Function

The Lower Extremity Battery (LEP: timed 4-meter walk, timed chair stand, and balance test) will be performed at baseline, 4 months and 12 months (Table 11 A). This test will be conducted by the study coordinator before the HD session since performance scores can be affected after a single HD treatment [Tawney, 2004]. The study coordinators will be trained by an experienced person familiar with the methods of this test prior to study start.

For the LEP, performance scores will be derived for each test with a score of 0 assigned to those unable to complete the test, and 4 indicating the highest level of performance. Ordinal categories for the 4-meter walk, chair stand, and balance test will be assigned based on reference tables developed for elderly people who participated in the EPESE study [Guralnik, 1994]. In addition, the individual scores for each of the 3 tests will be summed to create an overall LEP score (0-12). The LEP score incorporates missing data into the test results by assigning a score of 0 for missing values and for those unable to complete the test, while those who are able to complete the test are assigned a score according to a quartile of performance.

